## **Regulatory Sponsor:**

This study is an Investigator Initiated research trial. Each study site will be considered its own regulatory sponsor and is responsible for internal data monitoring and any study reporting required by ClinicalTrials.gov.

### **Introduction:**

Total knee arthroplasty is an effective orthopedic procedure to improve function, correct gait, and alleviate symptoms of late-stage arthritis in patients who have failed non-operative management. With constant introduction of various techniques for wound closure, assessment of closure times and outcomes will be a topic of marked importance.

The STRATAFIX (Ethicon, Johnson and Johnson, Somerville, New Jersey) Knotless Tissue Control suture device is a barbed suture that uses anchor technology to securely engage with the soft tissues while also eliminating the need for knots. The anchors, or barbs, are pressed out of the device core or formed within the core in a geometric pattern and arranged in a tapered manner to allow the device to pass through tissue in the direction toward the needle during closure. These knotless tissue control devices are deployed using a continuous technique, which we anticipate to be faster and more cost-effective than interrupted suturing.

## **Background and Significance/Preliminary Studies:**

Preclinical and biomechanical studies have demonstrated efficacy in cosmetic skin and deep tissue closures.[1], [2] In addition, barbed sutures have been shown to provide water-tight closure and wound strength comparable to or superior to closure with conventional sutures. Many comparative studies have been published contrasting barbed sutures to conventional closure techniques in multiple surgical fields. [3], [4]

Various studies have evaluated the outcomes of different barbed suture devices, however there are no reports assessing the length of closure times using STRATAFIX (Ethicon, Johnson and Johnson, Somerville, New Jersey) Knotless Tissue Control Devices during deep closure in total hip arthroplasty. Stephens et al. [5] performed a prospective randomized study of 500 total knee arthroplasty patients who received either barbed suture (250) or conventional sutures (250) for deep closure of the surgical wound. The mean operating time was significantly shorter in the barbed group as compared to conventional group (64.3 vs 68.1 minutes, p=<0.001). In a study of 80 TKA (61 barbed, 19 conventional deep sutures) and 54 THA patients (37 barbed, 17 conventional deep sutures), Smith et al. [6] found significantly shorter closure time in the barbed suture group (16.78 vs. 26.5 minutes, p<0.001). One study reports one the use of Stratafix suture for intracorporeal suturing in myomectomy. Giampaolino et al. [7] performed a prospective randomized study on 47 patients and evaluated the mean operative time for laparoscopic posterior myomectomy using Stratafix or conventional suture for intracorporeal suturing. There was a significant decrease in mean operative time associated with use of Stratafix suture as compared to conventional suture (66.3 vs 73 minutes, p=0.005).

This prospective randomized single-center study will examine the outcomes, mainly closure time, of deep closure during total knee arthroplasty using the STRATAFIX Symmetric PDS Plus (Ethicon, Johnson and Johnson, Somerville, New Jersey) barbed suture compared to interrupted VICRYL suture (Ethicon, Johnson and Johnson, Somerville, New Jersey).

# **Regulatory Sponsor:**

This study is an Investigator Initiated research trial. Each study site will be considered its own regulatory sponsor and is responsible for internal data monitoring and any study reporting required by ClinicalTrials.gov.

## **Study Design:**

In this prospective study examining the deep closure during total knee arthroplasty, active subjects will receive the STRATAFIX Symmetric PDS Plus (Ethicon, Johnson and Johnson, Somerville, New Jersey) suture while the control subjects will receive interrupted VICRYL suture (Ethicon, Johnson and Johnson, Somerville, New Jersey). Superficial closure will be the standard of care for both groups.

The purpose of this study is to compare end points (see below):

- The primary endpoint of the study will be closure time and operative time.
- **Secondary endpoints** will examine: wound complications, costs comparison between the two techniques.

Post-operatively, patients will be assessed at clinic visits at 6 weeks and 3 months. At these time points, we will assess (**Table 1**):

Table 1.

REQUIRED STUDIES	Pre-Op	Intra- operative	6 week post-op	3 month post-op
Informed Consent	X			
Length of surgery time		X		
Length of closure time		X		
Amount of suture material used		X		
Surgeon experience level		X		
Wound complications			x	X

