#### Methods

• A prospective randomized pilot study

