## **Data Analysis:**

Unless otherwise indicated, all testing of statistical significance will be two-sided, and a difference resulting in a p-value of less than or equal to 0.05 will be considered statistically significant. Also, after each analysis, General Linear Models (GLM) will be used to control for possible confounders, including BMI, gender, age and ethnicity.

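### Closure time and operative time are jointly primary with no success rule and no deciding analysis, so the error rate of the primary claim is not fixed

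*Combined protocol and SAP*

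**What the plan says.** Study Design puts two measurements under one label: "The primary endpoint of the study will be closure time and operative time". Table 1 in the same section lists length of surgery and length of closure on separate rows, so they are two variables and not a composite.

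The Data Analysis section is the only statistical section. It makes all testing two-sided and says that "a difference resulting in a p-value of less than or equal to 0.05 will be considered statistically significant". It then says that "after each analysis, General Linear Models (GLM) will be used to control for possible confounders, including BMI, gender, age and ethnicity". It does not name the analysis that comes before the GLM.

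Background and Significance/Preliminary Studies gives closure time more weight: "This prospective randomized single-center study will examine the outcomes, mainly closure time, of deep closure during total knee arthroplasty". Study Design does not carry that emphasis over.

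Methods describes the trial as "A prospective randomized pilot study", and Sample sets 60 subjects without a power calculation.

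**The concern.** Three things are missing: whether one or both times must be significant, the order or alpha split if they are tested separately, and which of the two analyses decides. Read literally, the plan produces up to four p-values (two times, each with an initial and an adjusted analysis), each compared with 0.05.

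A split result is realistic. Closure time may differ clearly while operative time does not, or the initial and adjusted results may fall on opposite sides of 0.05. The plan could not then say whether the primary objective was met, and the choice would be made after the data are seen. What is at stake is whether the 0.05 in the plan describes the chance of a false primary claim.

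**Working it through.** The plan gives no error rate, power, effect size or SD, and the 60 has no derivation, so it has no figure of its own to reproduce.

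**Inputs from the plan.** Two primary times; two-sided 0.05 for each test; 60 subjects allocated 1:1 (Randomization procedures), so 30 per arm if balanced.

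**Assumptions.** Correlation ρ between the two times: 0 to 0.9, with the limit at 1. Share of outcome variance explained by the covariates (R²): 0 to 0.3. Initial analysis: an unadjusted two-group comparison.

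**Step 1: either time can win, one fixed analysis.** With no true difference in either time, P(either) = 1 − P(|Z₁| < 1.96 and |Z₂| < 1.96), with Z₁ and Z₂ bivariate normal. At ρ = 0 this is 1 − 0.95² = 0.0975.

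**Step 2: both must win, one fixed analysis.** P(both) = 0.05 + 0.05 − P(either). If only one time is truly null, a false claim requires that one null test to be significant, so the rate cannot exceed 5%.

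**Step 3: Holm.** With both null, any claim requires the smaller p-value to be at most 0.025. At ρ = 0 this is 1 − 0.975² = 0.0494.

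| ρ | Either wins | Both must win | Holm |
|---|---|---|---|
| 0 | 9.75% | 0.25% | 4.9% |
| 0.5 | 9.1% | 0.9% | 4.7% |
| 0.9 | 7.0% | 3.0% | 3.6% |

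Beyond 0.9 the either-wins rate keeps falling: 6.5% at ρ = 0.95 and 5% in the limit at 1.

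**Step 4: model left open, closure time alone.** This used simulated null trials with 30 per arm and four covariates (two continuous, two binary), 40,000 trials per setting, Monte Carlo standard error at most 0.18 percentage points. If either the unadjusted or the adjusted p-value may count, the rate is 6.1% to 7.7% over R² of 0 to 0.3. With the adjusted model fixed in advance it is 4.7% to 5.2%, which is 5% within simulation error.

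**Step 5: what the alternatives cost in power.** The only guides are the cited studies' results, and a result reported as p < 0.001 gives only an upper bound on the SD (assuming an equal-variance t-test).

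- Closure time, cited knee and hip study ("16.78 vs. 26.5 minutes, p<0.001"): difference 26.5 − 16.78 = 9.72 minutes; groups 61 + 37 = 98 and 19 + 17 = 36; critical t on 132 df = 3.366. SD ≤ 9.72 / 3.366 / √(1/98 + 1/36) = 14.8. At 30 per arm and that SD, power is 70% at 0.05, 60% at 0.025, and 60% to 68% under Holm. At an assumed SD of 10 it is 96% at 0.05 and 93% at 0.025.
- Operative time, cited knee trial ("64.3 vs 68.1 minutes, p=<0.001"): difference 68.1 − 64.3 = 3.8 minutes; 250 per group; critical t on 498 df = 3.310. SD ≤ 3.8 / 3.310 / √(2/250) = 12.8. Power at 30 per arm is about 20%.

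Because the SDs are upper bounds, the 70%, 60% and 20% are floors for the stated differences.

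**The case against.** The strongest reply is that the text does not commit the trial to an either-can-win rule. Study Design uses the singular for the primary endpoint and joins the two times with *and*, which can be read as requiring both. Under one fixed analysis that reading has no inflation. The Background wording supports a third reading, with closure time leading. The GLM is introduced to control for confounders and can fairly be taken as supportive. All of this stands, and it is why the percentages are conditional. It does not close the gap: three readings with different error rates are all compatible with the text.

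The pilot label is the second reply. Strict multiplicity control over two related times in 60 subjects, with no power claim, is less pressing than in a confirmatory trial. That also stands, and it limits the weight of the point. It does not remove it, because Data Analysis still declares significance at 0.05 and the plan offers no feasibility or estimation criterion in its place.

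Third, fixing the listed covariates is not beyond question. The list is introduced with *including*, so it is open. Table 1 also collects surgeon experience, which may predict closure time. The coding of ethnicity is not given: with one column per covariate the model leaves 60 − 6 = 54 residual degrees of freedom, and each further category costs one more. These points should be settled when the model is named. They do not argue for leaving it unnamed.

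**Conclusion.** The point holds as a statement that the primary error rate is unspecified, not that it is necessarily inflated. It exceeds 5% if either time can carry the claim, and also if the model is chosen afterwards. It does not if both times must win under one fixed analysis. The sizes rest on assumed correlations and R², and on the inference that the initial analysis is unadjusted.

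A reader might infer two stronger things that the documents do not support. One is that 7.0% is the least possible inflation when either time can win. That figure only reflects stopping at a correlation of 0.9; the plan gives no correlation, and the rate tends to 5% as it tends to 1. The other is that all four p-values are in play, which in simulation gives rates up to 14.6% (ρ = 0, R² = 0.3). Nothing in Data Analysis says that either result may be picked afterwards, and that figure depends heavily on the assumed covariate structure.

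For a 60-subject pilot with no stated power, this is a cheap improvement: a clarification, not a redesign.

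**What to change.** In Study Design, name closure time as the single primary endpoint, consistent with the Background section. Make operative time secondary, reported with a 95% confidence interval.

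In Data Analysis, name the linear model adjusted for BMI, gender, age and ethnicity as the deciding analysis for both times. Close the covariate list, state how ethnicity is coded, and label the other analysis supportive.

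If both times are to stay primary, state either a both-must-win rule or a Holm procedure, with the same adjusted model deciding for each.

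The change is two or three sentences, made before results are seen, with no change to data collection or sample size. The cost is that operative time loses its primary claim. If both stay primary, the cost is some power: under Holm no more than testing each time at 0.025, and under both-must-win an amount that depends on the power for operative time, which the cited studies leave largely unknown.

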#### Methods

• A prospective randomized pilot study

## Sample

• 60 subjects for a pilot study

### Inclusion Criteria:

- 1. Males and females, between the ages of 18 to 80 years at the time of signing the informed consent document.
- 2. Understand and voluntarily sign an informed consent document prior to any study-related assessments/procedures are conducted.
- 3. Able to adhere to the study visit schedule and other protocol requirements.

- 4. Able to fluently speak and understand the local language
- 5. If female, is non-pregnant (negative pregnancy test results at the baseline/randomization visit) and non-lactating.
- 6. End-stage osteoarthritis patients planning to undergo primary total knee arthroplasty
- 7. BMI less than 40 kg/m^2

### Exclusion Criteria:

- 1. BMI greater than or equal to 40 kg/m2.
- 2. History of known bleeding disorder.
- 3. History of medical co-morbidity that may result in poor wound healing (i.e. diabetes mellitus, peripheral vascular disease).
- 4. Patients <18 or >80 years of age.
- 5. Patients who are prisoners.
- 6. Mentally unable to sign informed consent.
- 7. Has an uncontrolled illness that, in the opinion of the investigator, is likely to cause the patient to be withdrawn from the trial or would otherwise interfere with interpreting the results of the study.

# **Screening and Recruitment: Informed Consent**

Informed consent will be obtained by one of the study coordinators/co-investigators during a clinical visit prior to procedure in the privacy of an examination room or an office. Patients will be informed about the study and inquired about their interest to participate. A consent document will be given and key parts of the research study will be explained in lay-terms to the patient to ensure full understanding. Any questions regarding the research study will be answered at that time. It will be emphasized that participation is voluntary. Those patients who are willing to participate will be asked to sign the consent document along with the consenting researcher. A signed copy of the consent document will be handed to the patient while another copy is kept in their study file.

In the event that an approach prior to the day of surgery is not feasible, same day of procedure consenting will be attempted. Patients will be contacted by telephone (see phone script), and those interested in participating in the study will be informed about what is involved, the follow-up visit, and that participation in the study is strictly voluntary, and will not affect the scheduling of their upcoming surgery. If the patient is interested in participating, the patient can be either mailed or emailed a copy of the informed consent form, and then arrangements will be

made to complete the informed consent process prior to the patient being taken back into the preoperative area on the day of surgery. The patient will be asked to come to the hospital on the day of surgery earlier than the time they were told to arrive by surgical scheduling in order to make sure there will be adequate time to discuss the study, including what is involved, risks, benefits, and alternatives. We do not believe that an eventual approach on the same day of procedure would represent an added stress for the patient or delay the start of the procedure. Similar to obtaining informed consent prior to the day of procedure, the process will occur in a private setting with ample time to discuss the study's implications, risks, benefits, and alternatives. No procedures or tests will be conducted on the screening visit after consenting the patient.

# **Randomization procedures:**

Patients will be randomized to either arm of the study as follows: sealed envelopes in a random order will be used to place study participants in either the barbed suture arm or in the traditional suture arm of the study. Patients will be randomized in a one to one ratio. At the commencement of each arthroplasty, a random envelope will be drawn which dictated the type of suture to be used, thus blinding the patients to the type of suture they received.

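### The operator is neither coded nor fitted in the models for the two primary times, which gives up some precision at 60 patients

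*Combined protocol and SAP*

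**What the plan says.** All references are to the combined protocol and SAP.

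- **Randomization procedures.** "sealed envelopes in a random order will be used to place study participants in either the barbed suture arm or in the traditional suture arm", and "Patients will be randomized in a one to one ratio". The draw is made in theatre: "At the commencement of each arthroplasty, a random envelope will be drawn". No blocks and no strata are described.
- **Study Design.** "The primary endpoint of the study will be closure time and operative time". In Table 1 the intra-operative column has both times, the amount of suture and "Surgeon experience level". No item identifies the operating surgeon or the person who closes.
- **Data Analysis.** After each analysis, "General Linear Models (GLM) will be used to control for possible confounders, including BMI, gender, age and ethnicity". Neither operator identity nor experience level is named.
- **Sample.** "60 subjects for a pilot study". No power, target difference or standard deviation is given, and neither is the number of surgeons.

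**The concern.** Both primary outcomes are durations that depend on the hands doing the work. Recording experience level case by case makes sense mainly if operators vary, yet that item is used in neither the allocation nor the analysis. Experience level is also only a partial stand-in, because two operators at the same level can work at different speeds. Without an identity code, an operator term cannot be fitted from the data that Table 1 lists.

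What is at stake is the width of the confidence interval. Between-operator variance that a model could remove stays in the error, and a trial of 60 has little precision to spare.

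**Working it through.** The plan states no figure to reproduce on this point.

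**Inputs from the documents:** 60 patients at 1:1, taken as exactly 30 per arm. Background and Significance cites an operative-time difference of 68.1 − 64.3 = 3.8 min and a closure-time difference of 26.5 − 16.78 = 9.72 min.

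**Assumptions:** five operators with 12 cases each; total variance 1; operator share ρ of that variance, from 0 to 0.4.

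**1. Variance of the arm difference as planned (no strata, no operator term).**
- One operator's count in an arm is hypergeometric, with variance 30 × 0.2 × 0.8 × 30/59 = 2.441.
- The operator part is ρ × 5 × 4 × 2.441/900 = 0.0542ρ.
- The residual part is (1 − ρ) × 2/30 = 0.0667(1 − ρ).

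**2. Variance with an operator term, unstratified envelopes.**
- This is (1 − ρ) × E[1/S], where S is the sum over operators of n₁n₀/12, with n₁ and n₀ the operator's cases in each arm.
- The mean of S is 5 × (36 − 2.441)/12 = 13.98. Averaging 1/S over 400,000 random allocations gives 0.0717.

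**3. Variance with the term and perfect 6:6 balance for every operator.** S = 15, so the variance is (1 − ρ)/15.

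| ρ | As planned | Term only | Variance ratio | Cut in SE |
|---|---|---|---|---|
| 0 | 0.0667 | 0.0717 | 0.93 | −4% |
| 0.1 | 0.0654 | 0.0645 | 1.01 | 0.7% |
| 0.2 | 0.0642 | 0.0574 | 1.12 | 5% |
| 0.4 | 0.0617 | 0.0430 | 1.43 | 16% |

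The variance ratio less 1 is the equivalent increase in sample size: 12% at ρ = 0.2 and 43% at ρ = 0.4. The term breaks even where (1 − ρ)(0.0717 − 0.0667) = 0.0542ρ, which is ρ of about 0.085. It takes four degrees of freedom (58 to 54), which moves the two-sided 5% critical value only from 2.002 to 2.005.

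**4. What stratification adds to the term.** 1 − √(0.0667/0.0717) is about 3.6% of the standard error at any ρ, and only with perfect balance. Term and stratification together give variance ratios of 0.0642/0.0533 = 1.20 at ρ = 0.2 and 0.0617/0.0400 = 1.54 at ρ = 0.4.

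**5. Predictability.** Suppose a surgeon with 12 cases always guesses the arm that is behind so far. With per-surgeon blocks of 2 and 4 in random order, about 72% of guesses are right. For a surgeon who tracks only their own cases from one 30/30 list, about 52% are right.

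**6. Size of a chance split.** An operator with 12 cases is split 8:4 or worse with probability 0.333, and 9:3 or worse with probability 0.104. A group with 30 of the 60 cases is split 18:12 or worse with probability 0.196. If that group is 5 min slower (assumption), an 18:12 split shifts the arm difference by (18/30 − 12/30) × 5 = 1.0 min. That is 1.0/3.8 = 26% of the cited operative-time difference and 1.0/9.72 = 10% of the cited closure-time difference.

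**7. Validity.** A separate simulation used 2, 4 or 6 surgeons, shares of 0.1 to 0.5 and 4,000 trials per setting. The unadjusted estimate was unbiased within simulation error (at most 0.005 SD), with type I error of 4.7% to 6.0%.

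**The case against.** The strongest case on the other side is that this is an efficiency option in a pilot, not a correction. Randomization already protects validity, and chance splits are already part of the standard error. The documents do not give the number of operators; with one there is nothing to gain, and below a share of about 8.5% the term costs a little. The covariate list begins with the word for including, so an operator term is not ruled out.

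Most of this stands. It limits the size of the point and shows that no validity defect is involved. It does not remove the point. An unnamed covariate is not prespecified, and choosing it after seeing the data invites selective adjustment. Nor can it be fitted if no code was recorded. The pilot label does not settle the matter either, because Data Analysis plans two-sided tests at 0.05.

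A reader might infer three stronger things that the documents do not support:

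- **That uneven splits of surgeons bias the comparison or could pass for the treatment effect.** The estimate is unbiased on average. The worked shift is about a quarter of the cited operative-time difference and a tenth of the closure-time one. A shift comparable to those differences would need a much larger pace gap between operators than the 5 min assumed here, and the documents give no such figure.
- **That the envelopes must be stratified by surgeon.** That half adds least. In a theatre where the team sees each allocation, it trades about 3.6% of the standard error for much easier guessing. It also balances the surgeon, who may not be the person who closes; the documents do not say who closes.
- **That one common envelope supply is specified.** The section is silent on strata; a single supply is only the natural reading.

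**Conclusion.** The point holds as a modest loss of precision. No operator stratum is stated, no operator term is named, and no operator code is listed, so between-operator variance stays in the error of both primary times. With five equal operators explaining 20% to 40% of the variance, the term alone cuts the standard error by about 5% to 16%. The operator count, the equal caseloads and the variance share are all assumptions. At a 10% share the gain is under 1%; with one operator it is zero; if several operators do not differ at all, the term costs about 4%. Recording the codes and prespecifying the term is worth doing. The absence of stratification is not in itself an error.

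**What to change.** 1. **Study Design, Table 1:** add to the intra-operative column a code for the operating surgeon and a code for the person who closes.
2. **Data Analysis:** prespecify operator as a factor in the General Linear Model for each primary time, using the closer for closure time and the operating surgeon for operative time. State in advance how low-volume operators are pooled, or use a random operator effect if there are many. If a single operator will do every case, say so and omit the term.
3. **Randomization procedures (optional):** envelope sets per surgeon may be considered, weighing the small extra gain against predictability. If they are not used, no change is needed here on this account.

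The cost is one or two codes per case and a few degrees of freedom, plus the small loss shown above if operators turn out not to differ. The codes should be in place before enrolment, because they are harder to recover later.

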### **Research Procedure:**

A medial parapatellar approach will be performed. All closures will be performed in 3 layers, with the knee in approximately 90° of flexion to minimize potential imbrication of the capsule. For the traditional closure (control group), the arthrotomy (deep layer) is repaired using number 1 Vicryl followed by closure of the intermediate layer with a 2-0 Vicryl and a subcutaneous layer with a 2-0 Monocryl followed by steri-strips and adhesive.

For the active arm of the study, wound closure will be performed similarly in 3 layers with the use of barbed equivalents at every layer: STRATAFIX symmetric PDS Plus #1 will be used to close the capsule (See Table 2). The subcutaneous layer will be then closed with simple interrupted knots using number 2-0 braided absorbable sutures (Vicryl), followed by closure of the subcutaneous layer using a number 2-0 monofilament absorbable suture with inverted interrupted knots (Monocryl, Ethicon; Johnson & Johnson) followed by the use of steri-strips and adhesive (See table 2).

Closure with the bidirectional barbed suture involves starting at the midpoint of the wound and proceeded simultaneously both proximally and distally to the ends. At the ends of the wounds, the suture is backstitched at this subcuticular level (2-3 throws) toward the midpoint for

further reinforcement before bringing the needle out through the skin; the suture is then cut flush with the skin tissue at its free end. With each throw, the leading end of the suture is pulled with only enough tension to engage the barbs with the surrounding tissue, thereby locking the wound edges into approximation. As with the traditional closure and in concordance with our routine protocol, barbed closures were finished with skin steri-strips and adhesive.

Table 2: Suture Type for Closure Following Total Knee Arthroplasty.				
Layer	Control Group	Active Group		
Capsule	Vicryl #1 (J947H#1)	STRATAFIX (SXPP1A04#1)		
Subcutaneous	Vicryl 2-0 (J945H 2-0)	Vicryl 2-0 (J945H 2-0)		
Subcuticular	Monocryl 4-0 (Y496H)	Monocryl 4-0 (Y496H)		
Skin	Steri-strips, glue (Standard of care)	Steri-strips, glue (Standard of care)		

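### The suture envelope is drawn at the start of surgery, so the team can know the arm during a phase where it has no use but which counts toward operative time

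*Combined protocol and SAP*

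**What the plan says.** All references are to the combined protocol and SAP.

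- **Timing of allocation (Randomization procedures).** "At the commencement of each arthroplasty, a random envelope will be drawn which dictated the type of suture to be used". The only blinding described is of patients: "thus blinding the patients to the type of suture they received". The section does not say who opens the envelope, when the surgeon learns the arm, or that the content is withheld until closure.
- **Endpoints (Study Design).** "The primary endpoint of the study will be closure time and operative time". Table 1 lists "Length of surgery time" as an intra-operative item separate from closure time, and also lists "Surgeon experience level". No start or stop point is given for either clock.
- **Where the arms differ (Research Procedure and its Table 2).** One surgical approach is given for all patients. In the active arm, "STRATAFIX symmetric PDS Plus #1 will be used to close the capsule"; the control arm has Vicryl there. Table 2 shows the same materials in both arms for the remaining layers.
- **Size (Sample).** "60 subjects for a pilot study", randomized 1:1.

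**The concern.** The allocation is drawn well before it is needed. From the start of the operation until capsule closure both arms receive the same surgery, yet the team can know throughout which suture will be used. That phase adds to operative time, and its length depends partly on the pace of an unblinded team. The Introduction already states an expectation that the barbed technique will be faster.

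There are two routes to bias:

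1. **Pacing before closure.** This can reach operative time only, because closure time starts later.
2. **Choice of closing operator with the arm known.** This could reach both closure time and operative time. Table 1 records surgeon experience, which suggests that it may vary, but the covariates named in Data Analysis (BMI, gender, age, ethnicity) do not include it.

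The only benefit the protocol attaches to the procedure is patient blinding, and a later opening would serve that equally well.

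**Working it through.** The plan gives no power, effect size or SD, so it has no figure of its own to reproduce. The argument rests on setting the sections side by side. The arithmetic only gives a sense of scale.

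**Logic of the sections**

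- The envelope is drawn at the start of the operation, and no later disclosure step is described. On the natural reading, the team can know the arm from then on.
- The arms first differ at the capsule. The text of Research Procedure implies barbed suture in more layers than Table 2 shows, and the two must be reconciled. On either reading the pre-closure phase is the same in both arms.
- Surgery time is recorded separately from closure time. On its ordinary meaning, surgery time includes the pre-closure phase.

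**Scale against the cited effect**

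- Input: operating times of 64.3 and 68.1 minutes, 250 patients per group, p<0.001, from the knee trial described in Background and Significance/Preliminary Studies.
- Difference: 68.1 − 64.3 = 3.8 min.
- Assumed pre-closure shift of 1 to 3 min: 1/3.8 = 26%; 3/3.8 = 79%.

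**A rough ceiling for the SD**

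The documents give no SD. If the cited p-value came from a two-sample t-test:

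- t(0.9995, 498 df) = 3.31, so SE ≤ 3.8/3.31 = 1.148 min.
- SD ≤ 1.148/√(2/250) = 12.8 min.

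This bounds total operating time in that study, not pre-closure time in this one. I use it only to choose an assumed range of 5 to 13 min for the pre-closure SD.

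**How well a check afterwards would work**

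With 60 patients at 1:1 there are 30 per arm. The 95% half-width for the difference in pre-closure time is t(0.975, 58 df) × √(2/30) × SD = 2.002 × 0.2582 × SD = 0.517 × SD.

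| Assumed SD (min) | 95% half-width (min) | Power, 3-min shift | Power, 1-min shift |
|---|---|---|---|
| 5 | 0.517 × 5 = 2.6 | 63% | 12% |
| 10 | 0.517 × 10 = 5.2 | 21% | 7% |
| 13 | 0.517 × 13 = 6.7 | 14% | 6% |

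Power is for a two-sided 5% t-test.

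**Effect on the operative-time test**

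Suppose the sutures make no difference but pre-closure time shifts by b = 2 min (assumed). With a normal approximation and SE = SD × √(2/30), the chance of a significant result is Φ(b/SE − 1.96) + Φ(−b/SE − 1.96). Here SD refers to operative time and is also assumed.

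- SD 5: SE = 1.291, b/SE = 1.549, rate 0.34.
- SD 10: SE = 2.582, b/SE = 0.775, rate 0.12.
- SD 20: SE = 5.164, b/SE = 0.387, rate 0.07.

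If the arm is revealed only at closure, knowing it cannot shift the earlier phase (b = 0), and the rate from this source stays at 0.05.

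**The case against.** The strongest reply is that the exposure is inferred. The text says the envelope is drawn, not that the surgeon reads it, and operative time has no defined start or stop. Both points are true. The claim is therefore only that the team can know the arm, and that operative time on its ordinary meaning covers the earlier phase. If delayed disclosure is already intended, one sentence saying so settles the matter.

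Second, the reach is narrow. The Background describes closure time as the main outcome, and pacing before closure cannot alter it. The surgeon must know the arm during closure, when the treatment effect arises, whatever the timing of the envelope. This stands, and it limits the pacing argument to operative time. Operative time is nevertheless named as primary. The operator-choice route could reach closure time, but the documents do not say that the operator is chosen after the draw.

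Third, the magnitudes are assumptions and no direction of bias is shown. That also stands: the figures show what a small shift could do, not that one will occur.

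Fourth, this is a 60-patient pilot, and drawing the envelope at surgery, after consent, does not harm concealment at enrolment. Both are fair. However, Data Analysis still plans significance tests at 0.05, and opening at closure would protect enrolment at least as well.

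**Conclusion.** The concern holds. As written, the plan lets the arm be known during a phase in which it has no use and which, on the ordinary meaning of operative time, counts toward a primary endpoint. The size of any resulting bias is unknown. Under the assumed 1 to 3 minute shift it could be a substantial fraction of the 3.8-minute effect cited as background. The separate recording of surgery time, closure time and experience permits a partial check, but at 30 per arm that check could easily miss a shift of this size. Prevention is the better protection. The change should be made: the risk to a primary endpoint is avoidable and the cost is very small. Confidence is moderate, because the moment of disclosure and the operative-time clock are both left unstated.

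**What to change.** Amend Randomization procedures so that the next sequentially numbered, opaque, sealed envelope is opened only when the team is ready to close the capsule. It should be opened after the closing operator and experience level have been recorded and before the closure clock starts, with the opening time logged. The numbering and opacity are ordinary concealment practice; the timing is what answers this point.

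Define the start and stop of surgery time and closure time on compatible clocks. Then compare pre-closure time (surgery time minus closure time) between arms as a partial check, reported with its confidence interval.

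The timing change needs one or two sentences. Both sutures must be at hand until closure, and the opening step must be kept outside the closure clock. The change reduces performance bias but does not remove it, since the arm is necessarily known during closure.
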